6. STATISTICAL METHODS OF ANALYSIS

6.1 General Principles

The statistical analyses will be performed by [REDACTED] with approval of the Sponsor, using SAS® Version 9.4 (or higher). All tables, figures and listings will be produced in landscape format.

In general, all data will be listed by subject and visit/time point where appropriate. The summary tables will be stratified by, or have columns corresponding to, treatment groups.

The total number of subjects in the treatment group (N) under the specified population will be displayed in the header of summary tables.

Data will be summarized using descriptive statistics for continuous variables. Unless otherwise specified, descriptive statistics will include number of subjects, mean, standard deviation, minimum, median, and maximum. Number of subjects with missing values will also be displayed, but only if non-zero. The minimum and maximum statistics will be presented to the same number of decimal places as the original data. The mean and median will be presented to one more decimal place than the original data. The standard deviation will be presented to two more decimal places than the original data.

In summary tables of categorical variables, counts and percentages will be displayed. The count [n] indicates the actual number of subjects in a particular category, which should always be less than or equal to the total number of subjects in the respective study group with known (non-missing) category [M]. Percentage will be obtained by: % = $n/M*100$. Unless otherwise specified, all percentages will be expressed to one decimal place.

All statistical tests will be two-sided at a significance level of $\alpha = 0.05$, unless otherwise indicated.

Baseline will be defined as the last assessment, scheduled or not, prior to the first dose of the study drug, unless otherwise specified. This notion of baseline will also be referred to as Part I baseline. Part II baseline will be defined as the last assessment, scheduled or not, prior to the first dose of the study drug in Part II. Part II baseline will be used in analysis of findings collected in Part II for subjects initially randomized to Placebo and re-randomized to SCD-044

(█ mg or █ mg) in Part II. Throughout this SAP, if the word “baseline” is used without qualification “Part I” or “Part II”, it will refer to Part I baseline.

In by-visit summaries, only data collected on scheduled visits/time points will be summarized. Data from unscheduled assessments will be included in listings and may be used in determination of baseline if applicable.

Relative days will be calculated relative to date of first dose of the study drug. Relative days will be calculated as follows only when the full assessment date is known (i.e., partial dates will have missing relative days).

For assessment on or after the day of first dose of the study drug:

Relative Day = Date of Assessment – Date of First Dose of Study Drug+1.

For assessment before the day of first dose of the study drug:

Relative Day = Date of Assessment – Date of First Dose of Study Drug.

All dates will be displayed in DDMMYY format.

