6.1.3 Handling of Withdrawals and Missed Data

In the primary analysis of the primary and the key secondary endpoint subjects with missing endpoint will be treated as non-responders. For more details see section 6.9.1.1. Last Observation Carried Forward (LOCF) and Active Treatment Worst Case (ATWC)

imputations will be explored in the sensitivity analyses (see section 6.9.1.2). All other endpoints will be summarized as collected without imputations.

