6.9 Efficacy Analyses

6.9.1 Analysis of the primary and key secondary endpoints

6.9.1.1 Primary analysis

The primary analysis will be performed on the ITT population.

Subjects in the ITT population with missing EASI at Week 16 or missing baseline will be imputed as non-responders for the primary endpoint. Similarly, subjects in the ITT population with missing vIGA at Week 16 or missing baseline will be imputed as non-responders for the key secondary endpoint.

Additionally, the subjects with intercurrent events, i.e. those who took any rescue medications (systemic or topical) prior to Week 16, took any prohibited medications prior to Week 16 (as determined by blinded data review) and discontinued the study drug prior to Week 16 will be considered non-responders for both the primary and key secondary endpoint. Subjects will be known to take systemic rescue medications prior to Week 16 if this is recorded at the “Rescue Medications” CRF or “Concomitant Medications” CRF or the subject attended any of “Systemic Rescue Medications Visits” 7 to 10. Topical rescue medications will be identified through a review of the “Concomitant Medications” CRF.

For both primary and key secondary endpoint the number and percentage of subjects achieving the endpoint will be provided. Comparisons between each active group and the placebo group will be performed pairwise. Each comparison will be done using Cochran-Mantel-Haenszel (CMH) test stratified [REDACTED]

If all strata have no subject in one of the treatment groups, a value of 0.1 will be added to all cells in the corresponding table in order to prevent dividing by 0, as suggested in Greenland and Robins (1985). The estimates of Mantel-Haenszel common risk (response rate) difference between each active dose group and placebo, along with 95% confidence interval, will be provided. The p-value from the Breslow-Day test for homogeneity of strata will also be provided. If the p-value of the Breslow-Day test is ≥ 0.05 , the treatment-by-strata interaction is not significant. In the case of heterogeneity between the strata, in-depth analysis will be conducted to understand the source of the interaction; Fisher’s exact test will be used instead of CMH.

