6.9.2.2 Binary endpoints

Binary endpoints include:

- EASI50, EASI75, EASI90, EASI100 responses (i.e., reduction of at least 50%, 75%, 90% and 100% from baseline in EASI)
- vIGA response (achieving vIGA score of “clear” or “almost clear” on a 5-point vIGA scale with at least two-grade reduction from baseline)
- achieving ≥ 4 -point or ≥ 3 -point improvement in the severity of itching recorded in PP-NRS from baseline
- SCORAD50 and SCORAD75 responses (i.e., reduction of at least 50% and 75% from baseline in total SCORAD score)
- achieving ≥ 4 -point or ≥ 3 -point improvement in the frequency of itching recorded in PP-NRS from baseline
- achieving PGIC improvement
- achieving DLQI total score 0 or 1 at Weeks 16 and 32

Note that for all binary endpoints above that involve change from baseline or percent change from baseline, Part II baseline will be used for the groups Placebo/SCD-044 █ mg and Placebo/SCD-044 █ mg, while Part I baseline will be used for the other treatment groups.

Number and percentage of subjects achieving these endpoints will be presented by treatment group along with 95% confidence interval for percentages based on binomial proportion.

The percentage of subjects achieving EASI75, EASI50, vIGA and SCORAD75, SCORAD50 responses will be presented graphically.

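### Responder rates outside the primary analysis are observed-case rates with no intercurrent-event rule, so they can disagree with the Week 16 primary and key secondary results and can overstate later response

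*SAP*

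**What the plan says.** SAP 6.1 (General Principles) gives the general rule for tables of categorical variables: "Percentage will be obtained by: % = $n/M*100", where M is "the total number of subjects in the respective study group with known (non-missing) category [M"]. The full group size has a different place: "The total number of subjects in the treatment group (N) under the specified population will be displayed in the header of summary tables".

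SAP 6.1.3 confines imputation to two endpoints. For those, "In the primary analysis of the primary and the key secondary endpoint subjects with missing endpoint will be treated as non-responders". For the rest, "All other endpoints will be summarized as collected without imputations".

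SAP 6.9.1.1 applies the stricter rule at Week 16: "Subjects in the ITT population with missing EASI at Week 16 or missing baseline will be imputed as non-responders for the primary endpoint", with a parallel rule for vIGA. Subjects who took rescue or prohibited medication before Week 16 are also failures, as are those who "discontinued the study drug prior to Week 16 will be considered non-responders for both the primary and key secondary endpoint".

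SAP 6.9.2.2 lists EASI-50/75/90/100 response, vIGA response, SCORAD-50/75 response and the itch responses among the other binary endpoints. It asks for counts, percentages and binomial confidence intervals, and adds: "The percentage of subjects achieving EASI75, EASI50, vIGA and SCORAD75, SCORAD50 responses will be presented graphically". It names no other denominator and no rule for intercurrent events. Its baseline rule for the placebo-to-active groups shows that it covers Part II.

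**The concern.** The same response, for example EASI-75, is measured by two rules in one report. The primary table keeps every randomized subject. The 6.9.2.2 tables keep only subjects with a value and disregard intercurrent events. SAP 6.9.2 says that other endpoints use the ITT population, but this does not remove the difference, because the percentage base within that population is still M.

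Two things are at stake. First, a Week 16 EASI-75 or vIGA rate in a 6.9.2.2 table can differ from the reported primary or key secondary rate. Second, this is a dose-ranging study with treatment up to Week 32, and its later response rates will be read for durability by dose. If subjects doing poorly leave more often, the observed-case rate can rise, or hold up, with no added responder. If arms lose such subjects at different rates, their apparent order can shift. SAP 3.1 provides one route out for subjects doing poorly: discontinuation as a treatment failure when worsening makes it unsafe to continue.

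No visible analysis gives a response rate after Week 16 on all randomized subjects. The MMRM stops at Week 16, the LOCF, worst-case and tipping-point analyses concern the Week 16 endpoints, and the time-to-response analysis records first attainment, not persistence.

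**Working it through.** The visible text states no response rate, dropout rate or power, so there is no figure of the plan to reproduce. The check compares the SAP formula with the all-randomized rate.

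**Inputs from the documents.** About 240 subjects (Protocol 4.1) in a 3:1:1:3 ratio (SAP 3.1). The placebo and high-dose arms have 240 × 3/8 = 90 each; the low and intermediate arms have 240 × 1/8 = 30 each.

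**Assumptions, not from the documents.** 27 of 90 subjects are responders at Week 16 (p = 30.0%). A share d of 10%, 20% or 30% is missing at a later visit. Nobody's status changes except by leaving. Counts of leavers who were responders are rounded to whole subjects.

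**Formulas.** Observed-case rate = n/M, with M = N(1 − d). Fixed-denominator rate = n/N, with missing as non-response. If only non-responders leave, n stays at Np and n/M = p/(1 − d). That is the upper bound for the effect of missing data under these assumptions.

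| Missing | Leavers all non-responders, n/M | Leavers at half the arm rate, n/M | Leavers at the arm rate, n/M | Leavers at the arm rate, n/N |
|---|---|---|---|---|
| 9 (10%) | 27/81 = 33.3% | 26/81 = 32.1% | 24/81 = 29.6% | 24/90 = 26.7% |
| 18 (20%) | 27/72 = 37.5% | 24/72 = 33.3% | 22/72 = 30.6% | 22/90 = 24.4% |
| 27 (30%) | 27/63 = 42.9% | 23/63 = 36.5% | 19/63 = 30.2% | 19/90 = 21.1% |

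In the first scenario n/N stays at 27/90 = 30.0% throughout. An arm of 30 with 9 responders gives the same percentages there: 9/27, 9/24 and 9/21. If only responders leave, n/M falls: 18/81 = 22.2% with 9 missing and 9/72 = 12.5% with 18 missing.

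**Same visit, Week 16.** Let 27 of 90 be responders by the primary rule (30.0%).

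- With 9 missing, n/M is 27/81 = 33.3%; with 18 missing, 27/72 = 37.5%.
- Suppose also that 4 subjects with an intercurrent event have a qualifying assessment. The primary rule still gives 27/90 = 30.0%, but the 6.9.2.2 rule gives 31/81 = 38.3% or 31/72 = 43.1%.

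The second case shows that the missing intercurrent-event rule is a separate source of difference. It acts even where no value is missing.

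**The case against.** The case on the other side has real force.

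- **The rise is conditional.** A reader might infer that rates after Week 16 will rise as non-responders leave. The documents give no dropout rate and no pattern of who leaves. The treatment-failure clause in SAP 3.1 covers worsening that makes continuation unsafe, which is narrower than lack of response. If leavers respond like stayers, n/M is stable; if responders leave, it falls. This stands.
- **No switch of base within the series.** A reader might infer that the denominator changes from all randomized to M between Week 16 and Week 32. On the SAP's wording, the 6.9.2.2 rates use M at both visits. The change appears only when a later rate is set beside the primary table. This stands.
- **The graphs.** The n/M rule is written for summary tables. SAP 6.9.2.2 gives no denominator and no visits for the figures, and the shells are a separate document (SAP 9). That the graphs use M is an inference. This stands.
- **Other durability evidence.** Week 32 responder rates are not the only visible evidence. SAP 6.9.2.1 summarizes EASI change by visit, and SAP 6.9.2.3 gives vIGA categories and shifts at each post-baseline visit. Some endpoint text is redacted. This stands, although those summaries are also not imputed.
- **Recoverability.** Counts and N are displayed, so a reader can compute n/N. This stands only in part: n/N computed that way would still count as responders those who had an intercurrent event and a qualifying assessment.
- **The alternative has its own bias.** With 30% missing and leavers responding at the arm rate, n/N drops from 30.0% to 21.1%. This is a reason to show both rates, not to keep only one.

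**Conclusion.** The concern holds in a limited form. Under SAP 6.1, 6.1.3 and 6.9.2.2 together, the responder rates outside the primary analysis are observed-case rates without the composite strategy of the primary and key secondary estimands. It follows from the text that Week 16 EASI-75 and vIGA rates shown under 6.9.2.2 can differ from the primary and key secondary results. In the graphs this follows only if they use the same rule.

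Inflation of later rates is possible, not established. It requires leavers to respond less often than stayers, and its size is unknown because no dropout rate is given. For an assumed 30.0% response and 10–30% missing, it ranges from about none to 42.9%, the latter only if every leaver is a non-responder. The factor 1/(1 − d) is therefore a ceiling on the effect of missing data, not an estimate of it.

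The primary and key secondary tests are not affected. SAP 6.1.2 draws no inference from p-values for other endpoints, and Part II has no placebo group. The harm is to the descriptive picture of response over time and by dose, and to agreement between tables. That justifies a change to the SAP, but it does not threaten the trial's main conclusion.

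**What to change.** In SAP 6.9.2.2, with a matching exception in SAP 6.1 and 6.1.3:

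- Report each responder endpoint at each visit on a fixed denominator. Use all randomized subjects for Part I visits, and for the SCD-044 arms throughout. For the switch groups after Week 16, use all re-randomized placebo subjects.
- Count missing data, and the intercurrent events the SAP already lists, as non-response if they occur before that visit.
- Draw the EASI-75 and vIGA graphs on this basis, so that the Week 16 point equals the primary or key secondary result.
- Show the observed-case n/M rate beside it as supportive, with M printed at each visit.
- Label the switch groups as using the Part II baseline, and so not directly comparable with the Week 16 results.

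The cost is SAP wording and one derived flag per visit. The rates will look less favourable, and the fixed-denominator rate can understate response if leavers were responding. Showing both rates lets the reader see how much depends on that.

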10.4 Suspected Unexpected Serious Adverse Reactions (SUSARs)

An **Adverse Event or Suspected Adverse Reaction** is considered a SUSAR if it is serious, unexpected, and suspected. Prior to reporting to the applicable Regulatory Authorities, the Sponsor will evaluate the available evidence and to judge the likelihood that the drug actually caused the adverse event. The SUSAR must be reported to FDA within 15 days, or if fatal or life threatening, within 7 days, by the Sponsor. The Sponsor must report an adverse event as a suspected adverse reaction only if there is evidence to suggest a causal relationship between the drug and the adverse event. Additionally, potential Hy's law cases will be reported as SUSARs.

The Sponsor is responsible for reporting of suspected unexpected serious adverse reactions and notifying the relevant regulators (including the authorities in the EEA via EudraVigilance and the IRBs/IECs) and the Investigator sites within the specified timeframes of all SUSARs, as applicable per local requirements

The applicable Regulatory Authorities shall be notified by Sponsor Safety Physician of any SUSAR, as per local Regulatory Authorities guidelines and timeframe specified as per local regulation.

All participating Investigators, EC/IRB and other stakeholders shall be notified of any SUSAR by CRO's Medical Monitor as per local regulatory requirement.

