6.12.2 Laboratory tests

A central laboratory will be used for all assessments unless noted otherwise. Unscheduled laboratory assessments can be performed at discretion of the Investigator in response to AEs. The laboratory assessments include:

Hematology: at all on-site study visits a blood sample will be collected for total and differential WBC count, Absolute Neutrophil count (ANC), ALC, Platelet count, Hemoglobin, Hematocrit, Mean Corpuscular Volume (MCV) testing. Additionally, total WBC count with differential counts including ALC and ANC counts will be performed pre-dose and at 1h, 2h, 4h and 6h post-dose on Day 29 (Week 4).

Lipid profile: at the study visits 1, 2, 10 and 17 (Screening and study weeks 0, 16, and 32) a blood sample will be collected for LDL, HDL and total cholesterol and Triglycerides testing.

Clinical chemistry: at the study visits 1, 2, 7, 8, 10, 15, 16, and 17 (Screening and study weeks 0, 4, 8, 16, 20, 28, and 32) a blood sample will be collected for sodium, potassium, chloride, calcium, magnesium, bicarbonate, phosphate, blood urea nitrogen, random glucose, albumin, total protein, alkaline phosphatase, creatinine, ALT, AST, gamma glutamyl transferase (GGT), total bilirubin, conjugated bilirubin testing.

Coagulation profile: at the study visits 1, 2, 10, and 17 (Screening and study weeks 0, 4, 16, and 32) a blood sample will be collected for PT, INR, and aPTT testing.

Serology: at Screening visit a blood sample will be collected for: anti-VZV IgG, HIV antibodies, HBsAg, and HCV antibodies testing.

QuantiFERON Gold test: at Screening Visit a blood sample will be collected for TB antigens testing. A maximum of 2 QuantiFERON tests are allowed. A retest is permitted if the first is indeterminate; the result of the second test will be used. Chest X-ray should be performed for subjects with a positive or 2 successive indeterminate QuantiFERON test results; a chest X-ray is acceptable if performed within the past 3 months and available at a site along with an associated report.

Serum pregnancy test: at Screening Visit a blood sample will be collected for serum beta-hCG testing.

The following tests will be performed at a clinic site:

Urinalysis dipstick: at the study visits 1, 2, 10, and 17 (Screening and study weeks 0, 16, and 32) a urine sample will be collected for pH, specific gravity, protein, glucose, ketones, and blood testing.

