Microscopic exam may be performed at the local or central laboratory at the discretion of the Investigator if the dipstick is positive (i.e., trace or above).

Urine Pregnancy Test: at the study visits 2, 7, 8, 9, 10, 15, 16, 17, 18 (study weeks 0, 4, 8, 12, 16, 20, 28, 32, and 36) a urine sample will be collected in women of childbearing potential for hCG testing.

A positive result should be confirmed by a serum beta-hCG test. A confirmed positive urine pregnancy test during the treatment periods of the study requires immediate interruption of study drugs and the subject must be discontinued from the study.

Labs need not be repeated at baseline if these assessments for screening visit are performed within 2 weeks prior to the Visit 2.

For Hematology, Chemistry, and Coagulation profile the labs, which were abnormal and clinically significant at EOT, need to be repeated at safety follow-up visit.

[figure not shown]
Hematology, chemistry (including lipid profile), coagulation and continuous urinalysis parameters and their changes from baseline will be summarized descriptively by visit and treatment group. For WBC and differentials (absolute counts and percentages) percent change from baseline will also be summarized.

Additionally, hematology (WBC and differentials) results obtained during Day 29 (Week 4) visit will be summarized by timepoint with changes and percent changes from baseline.

Shifts from baseline among the categories Normal (within the reference range), Low (below the reference range) and High (above the reference range) will be presented by visit.

In the analyses of change from baseline and shifts from baseline above, Part II baseline will be used for the groups Placebo/SCD-044 [REDACTED] mg and Placebo/SCD-044 [REDACTED] mg, while Part I baseline will be used for the other treatment groups.

All results will be listed.

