6.12.8 Ophthalmological Examination

[figure not shown]
At the study Visits 1, 9 and 17 (Screening and study Weeks 12 and 32) a complete ophthalmologic examination will be performed by an ophthalmologist, including an ophthalmological history, best corrected visual acuity (Snellen chart), ophthalmoscopy (preferably slit-lamp) and Optical Coherence Tomography (OCT) assessment (measurement of central foveal thickness).

The following results of the ophthalmological examination will be summarized descriptively by eye (left or right), visit and treatment group:

- Best corrected visual acuity (Snellen denominator)
- OCT results: central fovea thickness

Number and percentage of subjects with presence of macular edema and/or uveitis will be presented by visit and overall across all visits (including both scheduled and unscheduled visits).

All ophthalmological examination data will be listed.

Number and percentage of subjects requiring monitoring beyond 6 hours will be provided along with reasons, treatment group and visit as well as overall across all visits.

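### The visible laboratory summaries omit post-baseline unscheduled results and give no per-arm counts of worst values, depth of lymphopenia or joint liver elevations

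*SAP*

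**What the plan says.** **Which data are tabulated.** SAP 6.1: "In by-visit summaries, only data collected on scheduled visits/time points will be summarized". It continues: "Data from unscheduled assessments will be included in listings and may be used in determination of baseline if applicable".

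**Why unscheduled tests exist.** SAP 6.12.2: "Unscheduled laboratory assessments can be performed at discretion of the Investigator in response to AEs".

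**What the laboratory tables contain.** SAP 6.12.2: "Hematology, chemistry (including lipid profile), coagulation and continuous urinalysis parameters and their changes from baseline will be summarized descriptively by visit and treatment group". It adds percent change for WBC and differentials, a Day 29 (Week 4) profile of the same parameters by time point, and one categorical display, presented by visit: "Shifts from baseline among the categories Normal (within the reference range), Low (below the reference range) and High (above the reference range"). All results are listed. SAP 6.1 fixes the content of the descriptive statistics: "Unless otherwise specified, descriptive statistics will include number of subjects, mean, standard deviation, minimum, median, and maximum".

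**Two points of comparison.** For macular edema and uveitis, SAP 6.12.8 asks for counts by visit and also "overall across all visits (including both scheduled and unscheduled visits"). Protocol 10.4 says of potential Hy's law findings that such "law cases will be reported as SUSARs".

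**The concern.** Post-baseline unscheduled results are the ones an investigator may order because a subject has become unwell. Under SAP 6.1 they inform no laboratory table.

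The categories are also coarse for this drug. Lymphocyte reduction is the intended effect (Protocol 1), so a Low lymphocyte cell mixes expected pharmacology with deep lymphopenia and cannot rank the doses on depth. A High ALT cell is the same whatever the multiple of the upper limit of normal (ULN). Potential Hy's law cases have a reporting route, but no visible table pairs transaminases with bilirubin.

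This is a dose-ranging study. What is at stake is whether the report can say, for each arm, how many subjects crossed a given limit. If it cannot, the laboratory tables may understate abnormalities by dose group.

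**Working it through.** The plan states no figure on this point, so there is none to reproduce. The check has four steps.

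**1. Where can a post-baseline unscheduled value appear?**

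| Visible laboratory output (SAP 6.12.2) | Organised by | Post-baseline unscheduled values? |
|---|---|---|
| Values and changes from baseline | Visit | No, under SAP 6.1 |
| Percent change, WBC and differentials | Summarised with the by-visit tables | No, under SAP 6.1 |
| WBC and differentials, Day 29 | Scheduled time point | No |
| Normal/Low/High shifts | Visit | No, under SAP 6.1 |
| Listing of all results | Subject | Yes |

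The visible text does not say whether Early Discontinuation results count as scheduled.

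**2. How often could a chemistry abnormality fall between scheduled draws?** SAP 6.12.2 places chemistry at Weeks 0, 4, 8, 16, 20, 28 and 32. The gaps are 4, 4, 8, 4, 8 and 4 weeks, 32 in total. Assume onset uniform over the 32 weeks and a duration of d weeks. The share lying wholly between draws is the sum over gaps of max(gap − d, 0), divided by 32.

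- d = 2: (2 + 2 + 6 + 2 + 6 + 2)/32 = 20/32 = 62.5%
- d = 3: (1 + 1 + 5 + 1 + 5 + 1)/32 = 14/32 = 43.8%
- d = 4: (0 + 0 + 4 + 0 + 4 + 0)/32 = 8/32 = 25%
- d = 6: (2 + 2)/32 = 12.5%
- d = 8: 0%

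The durations and the uniform onset are assumptions; the documents give neither. The result applies to chemistry only, because SAP 6.12.2 draws hematology at all on-site visits. It is the share that scheduled draws would miss. It is not the share that an unscheduled draw would catch and the rule would then leave out, which the documents do not allow one to estimate.

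**3. Can separate summaries of each parameter show a joint liver elevation?** Take three subjects with the same normal baseline. Assume ULN of 40 for ALT and 1.2 for bilirubin. For illustration only, call a case joint if ALT > 3 × 40 = 120 and bilirubin > 2 × 1.2 = 2.4.

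| | Subject 1 (ALT, bilirubin) | Subject 2 | Subject 3 | Mean ALT | Max ALT | Mean bilirubin | Max bilirubin | Joint cases |
|---|---|---|---|---|---|---|---|---|
| Set A | 200, 0.8 | 30, 2.6 | 25, 0.6 | 85 | 200 | 1.333 | 2.6 | 0 |
| Set B | 200, 2.6 | 30, 0.8 | 25, 0.6 | 85 | 200 | 1.333 | 2.6 | 1 |

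Each parameter has the same values in both sets, so every planned statistic and shift count agrees. The number of joint cases does not. The planned summaries cannot identify one.

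**4. Do the by-visit minimum and maximum fill the gap?** They show that one subject reached an extreme at a scheduled visit, not how many crossed a limit. They also compare poorly across unequal arms. With about 240 subjects (Protocol 4.1) allocated 3:1:1:3 (SAP 3.1), the arms are about 90, 30, 30 and 90. If two arms of 90 and 30 had identical distributions, the larger would hold the more extreme value with probability 90/(90 + 30) = 75%.

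**The case against.** The case against is substantial, and much of it stands.

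- **Shifts are not the only laboratory output.** By-visit minimum and maximum, percent change for WBC and differentials, and the Day 29 profile are also planned. A very high ALT or very low lymphocyte count at a scheduled visit would show as that visit's extreme.
- **A reader might infer that values from unscheduled draws never influence any table.** The documents do not support that. Protocol 10.1 counts a clinically significant abnormal laboratory finding as an AE, and SAP 6.12.1 tabulates AEs in detail. What is missing from the tables is the numeric value.
- **A reader might infer that potential Hy's law cases or deep lymphopenia would be hidden.** That too goes beyond the text. All results are listed, potential Hy's law cases are reported as SUSARs and so should also surface among serious and related events, and a DSMB has unblinded access (Protocol 12.6).
- **A reader might infer that unscheduled draws are selected for being abnormal.** SAP 6.12.2 says only that they may follow AEs at the investigator's discretion, and Protocol 3 allows unscheduled visits for any reason. Enrichment for abnormal values is likely, not stated.
- **The plan does not contradict itself.** Protocol 9.7 names shifts from baseline, and the SAP delivers them. The ocular count is an overall yes/no count, not a by-visit summary, so it does not conflict with SAP 6.1. It shows only that the remedy is already in use elsewhere in the SAP.
- **The public text is incomplete.** Some safety items in Protocol 9.7 are blacked out, a figure is missing just before the laboratory analysis text, and the shells are a separate document (SAP 9).

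The gap that remains is specific. AE tables depend on the investigator's judgement of significance and show a term, not a value. Listings carry no counts or denominators. SUSAR and DSMB review work during the trial and do not replace a planned summary by arm.

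**Conclusion.** The concern holds as a gap in presentation. In the visible SAP, post-baseline unscheduled laboratory results enter no laboratory summary table, and the only categorical display is Normal/Low/High by visit. No visible table gives per-arm counts of worst on-treatment values, depth of lymphopenia, or joint ALT/AST and bilirubin elevation. A plan that conceals such cases is more than the documents show.

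For chemistry, the share of short abnormalities that scheduled draws would miss runs from 62.5% at 2 weeks to 25% at 4 weeks, and reaches 0% at 8 weeks, under the stated assumptions. No comparable figure is offered for hematology, and the resulting understatement in the tables is not quantified.

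Confidence in the scheduled-only rule and the by-visit shifts is high, since both are explicit. Confidence that no threshold table exists is lower, because of the blacked-out text and the separate shells. The change is worth making but does not affect the efficacy conclusions.

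**What to change.** If the shells already contain such tables, a cross-reference in SAP 6.12.2 is enough. If not, add there, by treatment group and separately for Part I and Part II, worst-post-baseline summaries that use all scheduled, unscheduled and Early Discontinuation results. State that the scheduled-only rule in SAP 6.1 does not apply to them:

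- (a) shift from baseline to the worst value, using the Part I or Part II baseline that SAP 6.12.2 already assigns to each group;
- (b) number and percentage of subjects by prespecified limits for ALC, ANC, ALT, AST and total bilirubin. Use the protocol's own alert limits where they are defined; the Safety Lab Alerts are named in Protocol 7.1.4, but their limits are not visible in the public text. Otherwise use multiples of the ULN as display categories only, with no bearing on subject management;
- (c) a count and a plot of each subject's peak ALT or AST against peak bilirubin.

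The cost is some SAP wording and two or three extra tables or figures, with no new data collection. The downside is unequal testing: a subject tested more often has more chances of an extreme value. Show the number of tests per subject beside the tables, and keep the by-visit summaries as planned.
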